2.2. Study Design

This Phase 3, multicenter, randomized, double-blind study will be conducted at investigator sites in the United States.

Approximately 1780 healthy adults ≥ 65 years of age will be stratified by prior pneumococcal vaccine status (no previous pneumococcal vaccine [naïve], receipt of at least 1 dose of PPSV23 only, receipt of at least 1 dose of 13vPnC only, or receipt of at least 1 dose each of PPSV23 and 13vPnC) and randomized in a 1:1 ratio to 1 of 2 groups by center-based randomization. The coadministration group ([SIV+20vPnC]/saline) will receive SIV and 20vPnC at the same visit (Visit 1), followed 1 month later by administration of saline (Visit 2). The separate-administration group ([SIV+saline]/20vPnC) will receive SIV and saline at Visit 1, followed 1 month later with 20vPnC administered at Visit 2.

Blood will be collected at Visit 1 (prior to vaccination); at Visit 2 (prior to vaccination, 1 month after Visit 1); and at Visit 3 (1 month after Visit 2), to assess immunogenicity. Participants will be observed for 30 minutes after each vaccination and any reactions occurring during that time will be recorded as AEs.

Prompted local reactions (redness, swelling, and pain at the injection site) occurring at the 20vPnC/saline injection site within 10 days after vaccination (where Day 1 is the day of vaccination) and prompted systemic events (fever, headache, fatigue, muscle pain, and joint pain) and use of antipyretic/pain medications occurring within 7 days after vaccination (where Day 1 is the day of vaccination) will be collected via an e-diary after each vaccination visit (Visit 1 and Visit 2).

AEs will be collected from the signing of the ICD through Visit 3 (approximately 1 month after Visit 2). SAEs and NDCMCs will be collected from the signing of the ICD through 6 months after Visit 2.

3. ENDPOINTS AND BASELINE VARIABLES: DEFINITIONS AND CONVENTIONS

3.1. Primary Endpoints

3.1.1. Primary Safety Endpoints

- Prompted local reactions (redness, swelling, and pain at the injection site) within 10 days after each vaccination
- Prompted systemic events (fever, headache, fatigue, muscle pain, and joint pain) within 7 days after each vaccination
- AEs within 1 month after each vaccination
- SAEs up to 6 months after the last vaccination
- NDCMCs up to 6 months after the last vaccination

CCI [REDACTED]

[REDACTED]

[REDACTED]

[REDACTED]

[REDACTED]

[REDACTED]

CCI [REDACTED]

[REDACTED]	[REDACTED]	[REDACTED]	[REDACTED]
[REDACTED]	[REDACTED]	[REDACTED]	[REDACTED]
[REDACTED]	[REDACTED]	[REDACTED]	[REDACTED]
[REDACTED]	[REDACTED]	[REDACTED]	[REDACTED]

Severity and Maximum Severity

Redness and swelling will be measured and recorded in measuring device units (range: 1 to 21 and >21), and then categorized during analysis as mild, moderate, or severe based on the grading scale in Table 4. Measuring device units will be converted to centimeters according to the following scale: 1 measuring device unit = 0.5 cm. Pain at the vaccine injection site will be assessed by the participant as mild, moderate, or severe according to the grading scale in Table 4.

Table 4. Grading Scales for Local Reactions

Local Reaction	GRADE 1 Mild	GRADE 2 Moderate	GRADE 3 Severe	GRADE 4 ^a
Redness	5 to 10 measuring device units = >2.0 to 5.0 cm	11 to 20 measuring device units = >5.0 to 10.0 cm	>20 measuring device units = >10.0 cm	Necrosis or exfoliative dermatitis
Swelling	5 to 10 measuring device units = >2.0 to 5.0 cm	11 to 20 measuring device units = >5.0 to 10.0 cm	>20 measuring device units = >10.0 cm	Necrosis
Pain at injection site	Does not interfere with activity	Interferes with activity	Prevents daily activity ^b	Emergency room visit or hospitalization for severe pain at the injection site

Abbreviation: CRF = case report form.

Note: If the size of the redness and/or swelling falls between 2 measuring device units, the higher measuring device unit number will be recorded in the e-diary.

- a. Grade 4 assessment should be made by the investigator; Grade 4 will not be collected in the e-diary but will be collected as an AE on the CRF. The severity of the local reaction should be graded using the AE severity grading scale.
- b. Prevents daily activity, eg, results in missed days of work or is otherwise incapacitating.

For each local reaction after each vaccination, the maximum severity grade will be derived for the e-diary collection period (Day 1 through Day 10, where Day 1 is the day of vaccination) as follows:

maximum severity grade = highest grade (maximum severity) within 10 days after vaccination (Day 1 through Day 10) among severity grades reported for that local reaction in the e-diary.

CCI [REDACTED]

[REDACTED]

CCI [REDACTED]

[REDACTED]

The systemic events of headache, fatigue, muscle pain, and joint pain will be assessed by participants as mild, moderate, or severe according to the grading scale in [Table 5](#). Grade 4 will not be collected in the e-diary but will be collected as an AE on the CRF.

[REDACTED]

[REDACTED]

Table 5. Grading Scales for Systemic Events

	Mild Grade 1	Moderate Grade 2	Severe Grade 3^a	Grade 4^b
Fatigue (tiredness)	Does not interfere with activity	Some interference with activity	Prevents daily routine activity	Emergency room visit or hospitalization for severe fatigue
Headache	Does not interfere with activity	Some interference with activity	Prevents daily routine activity	Emergency room visit or hospitalization for severe headache
Muscle pain	Does not interfere with activity	Some interference with activity	Prevents daily routine activity	Emergency room visit or hospitalization for severe muscle pain
Joint pain	Does not interfere with activity	Some interference with activity	Prevents daily routine activity	Emergency room visit or hospitalization for severe joint pain

Abbreviation: CRF = case report form.

- Prevents daily routine activity, eg, results in missed days of work or is otherwise incapacitating; includes use of narcotics for analgesia.
- Grade 4 assessment should be made by the investigator; Grade 4 systemic events will not be collected in the e-diary but will be collected as AEs on the CRF. The severity of the systemic event should be graded using the AE severity grading scale.

Oral temperature will be collected in the evening daily for 7 days following each vaccination (Day 1 through Day 7, where Day 1 is the day of vaccination) and at any time during the 7 days that fever is suspected. Fever is defined as an oral temperature of $\geq 100.4^{\circ}\text{F}$ ($\geq 38.0^{\circ}\text{C}$). The highest temperature for each day will be recorded in the e-diary. In the event of a fever on Day 7, temperature will be collected daily until fever has resolved (1 day of temperature $< 100.4^{\circ}\text{F}$ [$< 38.0^{\circ}\text{C}$]) in order to collect a stop date in the CRF. Temperature will be measured and recorded to 1 decimal place.

Temperatures recorded in degrees Fahrenheit will be programmatically converted to degrees Celsius for reporting. Fever will be grouped into ranges for the analysis according to Table 6.

Table 6. Ranges for Fever

$\geq 38.0^{\circ}\text{C}$ to 38.4°C
$> 38.4^{\circ}\text{C}$ to 38.9°C
$> 38.9^{\circ}\text{C}$ to 40.0°C
$> 40.0^{\circ}\text{C}^{\text{a}}$

Note: Fever is defined as temperature $\geq 38.0^{\circ}\text{C}$.

- Participants reporting a fever $> 40.0^{\circ}\text{C}$ will be prompted to contact the study site.

CCI [REDACTED]

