8.2.2.1. Local Reactions

For the first 10 days following each study vaccination (Days 1 through 10, where Day 1 is the day of vaccination), the participants will be asked to assess redness, swelling, and pain at the blinded vaccine (20vPnC or saline) injection site and to record the symptoms in the e-diary in the evening. Redness and swelling will be measured and recorded in measuring device (caliper) units (range: 1 to 21+) and then categorized during analysis as mild, moderate, or severe based on the grading scale in [Table 1](#). Measuring device units can be converted to centimeters according to the following scale: 1 measuring device unit = 0.5 cm. Pain at the vaccine injection site will be assessed by the participant as mild, moderate, or severe according to the grading scale in [Table 1](#). The participant will be prompted to contact the investigator if he/she experiences a severe (Grade 3 or above) local reaction to assess the reaction and perform an unscheduled assessment or visit as appropriate.

Only an investigator is able to classify a participant’s local reaction as Grade 4, after physical examination of the participant or documentation from another medically qualified source (eg, emergency room or hospital record). If a participant experiences a Grade 4 local reaction, the investigator must immediately notify the sponsor. Site staff will educate the participants regarding signs and symptoms that would prompt site contact. Grade 4 reactions will be collected as an AE on the CRF. The event will be graded using the AE severity grading scale ([Section 10.3.4](#)).

The procedure for notification of the sponsor is provided in the ISF or equivalent.

Table 1. Grading Scales for Local Reactions

	Mild Grade 1	Moderate Grade 2	Severe Grade 3^a	Grade 4^b
Redness	5 to 10 measuring device units = >2.0 to 5.0 cm	11 to 20 measuring device units = >5.0 to 10.0 cm	>20 measuring device units = >10.0 cm	Necrosis or exfoliative dermatitis
Swelling	5 to 10 measuring device units = >2.0 to 5.0 cm	11 to 20 measuring device units = >5.0 to 10.0 cm	>20 measuring device units = >10.0 cm	Necrosis
Pain at injection site	Does not interfere with activity	Interferes with activity	Prevents daily activity ^c	Emergency room visit or hospitalization for severe injection site pain

Abbreviations: CRF = case report form; e-diary = electronic diary.

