Note: If the size of the redness and/or swelling falls between 2 measuring device units, the higher measuring device unit number will be recorded in the e-diary.

- Participants experiencing Grade 3 local reactions are required to contact the investigator site. In the event that the participant does not call, the investigator will call the participant.
- Grade 4 assessment should be made by the investigator; Grade 4 local reactions will not be collected in the e-diary but will be collected as AEs on the CRF. The severity of the local reaction should be graded using the AE severity grading scale in [Section 10.3.4](#).
- Prevents daily activity, eg, results in missed days of work or is otherwise incapacitating.

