9.4.2. Safety Analyses

Endpoint	Statistical Analysis Methods
Primary	
 • Descriptive statistics will be provided for each reactogenicity endpoint for each vaccine group. In each vaccine group, prompted local reactions from Day 1 through Day 10 and prompted systemic events from Day 1 through Day 7 after each vaccination will be presented by severity and cumulatively across severity levels. Descriptive summary statistics will include counts and percentages of participants with the indicated endpoint and the associated 2-sided Clopper-Pearson 95% CIs. • AEs, SAEs, and NDCMCs will be categorized according to MedDRA terms. A 3-tier approach will be used to summarize AEs. Under this approach, AEs are classified into 1 of 3 tiers: 
 (1) Tier 1 events are prespecified events of clinical importance and are identified in a list in the product’s safety review plan; (2) Tier 2 events are those that are not Tier 1 but are considered “relatively common”; a MedDRA preferred term is defined as a Tier 2 event if there are at least 1% of participants in at least 1 vaccine group reporting the event; (3) Tier 3 events are those that are neither Tier 1 nor Tier 2 events. 
For both Tier 1 and Tier 2 events, the 2-sided 95% CIs for the difference in percentage of participants reporting the events between the (SIIV+20vPnC)/saline group and the (SIIV+saline)/20vPnC group will be calculated using the Miettinen and Nurminen method. In addition, for Tier 1 events, the asymptotic p-values will also be presented for the difference in percentage of participants reporting the events, based on the same test statistic and under the assumption that the test statistic is asymptotically normally distributed.
 
There is no Tier 1 event identified for 20vPnC at this stage. For Tier 2 AEs, the between-group difference and 95% CIs will be calculated for 1 month after vaccination with SIIV and 20vPnC for the (SIIV+20vPnC)/saline group vs 1 month after vaccination with SIIV and saline for the (SIIV+saline)/20vPnC group, and for 1 month after vaccination with SIIV and 20vPnC for the (SIIV+20vPnC)/saline group vs 1 month after vaccination with 20vPnC for the (SIIV+saline)/20vPnC group. Descriptive summary statistics (counts and percentages and associated 2-sided Clopper-Pearson 95% CIs) will be provided for Tier 3 events, SAEs, and NDCMCs for each vaccine group.

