The investigator will make an assessment of intensity for each AE and SAE reported during the study and assign it to 1 of the following categories:

- Mild: An event that is easily tolerated by the participant, causing minimal discomfort and not interfering with everyday activities.
- Moderate: An event that causes sufficient discomfort and interferes with normal everyday activities.
- Severe: An event that prevents normal everyday activities. An AE that is assessed as severe should not be confused with an SAE. Severe is a category utilized for rating the intensity of an event; and both AEs and SAEs can be assessed as severe.

An event is defined as “serious” when it meets at least 1 of the predefined outcomes as described in the definition of an SAE, NOT when it is rated as severe.

GRADE	If required on the AE page of the CRF, the investigator will use the adjectives MILD, MODERATE, SEVERE, or LIFE-THREATENING to describe the maximum intensity of the AE. For purposes of consistency, these intensity grades are defined as follows:	
1	MILD	Does not interfere with participant's usual function.
2	MODERATE	Interferes to some extent with participant's usual function.
3	SEVERE	Interferes significantly with participant's usual function.
4	LIFE-THREATENING	Life-threatening consequences; urgent intervention indicated.

Assessment of Causality

- The investigator is obligated to assess the relationship between study intervention and each occurrence of each AE/SAE.
- A “reasonable possibility” of a relationship conveys that there are facts, evidence, and/or arguments to suggest a causal relationship, rather than a relationship cannot be ruled out.
- The investigator will use clinical judgment to determine the relationship.
- Alternative causes, such as underlying disease(s), concomitant therapy, and other risk factors, as well as the temporal relationship of the event to study intervention administration, will be considered and investigated.
- The investigator will also consult the IB and/or product information, for marketed products, in his/her assessment.
- For each AE/SAE, the investigator **must** document in the medical notes that he/she has reviewed the AE/SAE and has provided an assessment of causality.

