5.2.1. Analyses for Binary Data

Descriptive statistics for categorical variables (eg, proportions) are the percentage (%), the numerator (n) and the denominator (N) used in the percentage calculation, and the 95% CI where applicable.

The exact 95% CI for binary endpoints for each group will be computed using the F distribution (Clopper-Pearson).¹ The 95% CI for the between-group difference for binary endpoints will be calculated using the Miettinen and Nurminen² method.

The 3-tier approach will be used to summarize AEs. For both Tier 1 (if any are identified during the study) and Tier 2 events, a 95% CI for the between-group difference in proportions will be calculated based on the Miettinen and Nurminen method. In addition, for Tier 1 events (if any), the asymptotic p-values will also be presented for the difference in proportions, based on the same test statistic and under the assumption that the test statistic is asymptotically normally distributed. For Tier 3 events, counts and percentages for each vaccine group will be provided.

Between-group comparisons will be calculated for Tier 2 AEs specified as following:

- After vaccination with SIIV and 20vPnC for the (SIIV+20vPnC)/saline group vs after vaccination with SIIV and saline for the (SIIV+saline)/20vPnC group
- After vaccination with SIIV and 20vPnC for the (SIIV+20vPnC)/saline group vs after vaccination with 20vPnC for the (SIIV+saline)/20vPnC group

Between-group comparisons will be calculated for local reactions and systemic events specified as following:

- After vaccination with SIIV and 20vPnC for the (SIIV+20vPnC)/saline group vs after vaccination with 20vPnC for the (SIIV+saline)/20vPnC group

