6.1.1.1.1. Main Analysis

- Estimand: The percentage of participants reporting prompted local reactions (redness, swelling, and pain at the injection site) within 10 days after vaccination ([Section 2.1](#)).
- Analysis set: Safety population ([Section 4](#)).
- Analysis time point: Within 10 days after each vaccination.
- Analysis methodology: Descriptive statistics. The between-group difference and the corresponding 2-sided 95% CI will be calculated using the Miettinen and Nurminen method ([Section 5.2.1](#)).
- Intercurrent events and missing data: Missing values will not be imputed. CCI [REDACTED]
- Reporting results: Count and percentage of participants with the indicated endpoint and the associated 2-sided 95% Clopper-Pearson CI for each and any local reaction after vaccination in each vaccine group will be presented by maximum severity level. Between-group differences (see [Section 5.2.1](#)) in these percentages and their 2-sided 95% CIs will also be provided.

CCI [REDACTED]

[REDACTED]

[REDACTED]

[REDACTED]

[REDACTED]

[REDACTED]

CCI [REDACTED]

[REDACTED]

[REDACTED]

[REDACTED]

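### Does taking maximum severity of local reactions from the e-diary alone misreport Grade 4 reactions?

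*SAP*

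**What the plan says.** SAP Table 4 (section 3.1.1) and protocol Table 1 (section 8.2.2.1) grade redness, swelling and injection-site pain from 1 to 4. Grades 1 to 3 rest on measured size, or on interference with activity for pain. Grade 4 is a clinical finding or event: necrosis or exfoliative dermatitis for redness, necrosis for swelling, and an emergency room visit or hospitalization for pain.

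The two documents send Grade 4 down a separate route. Footnote a of SAP Table 4 says that "Grade 4 will not be collected in the e-diary but will be collected as an AE on the CRF". Protocol section 8.2.2.1 reserves the classification for the investigator and adds: "Grade 4 reactions will be collected as an AE on the CRF. The event will be graded using the AE severity grading scale". The footnote to protocol Table 1 repeats this: "The severity of the local reaction should be graded using the AE severity grading scale". On that AE scale (protocol section 10.3.4), Grade 4 means "Life-threatening consequences; urgent intervention indicated".

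For analysis, the SAP sorts the e-diary data into mild, moderate or severe and takes the maximum "among severity grades reported for that local reaction in the e-diary" over Days 1 to 10. SAP section 6.1.1.1.1 says that counts and percentages for each and any local reaction "will be presented by maximum severity level". Protocol section 9.4.2 says that prompted reactions "will be presented by severity and cumulatively across severity levels". SAP section 5.2.1 adds a comparison of the two groups, each after its 20vPnC injection: "Between-group comparisons will be calculated for local reactions and systemic events specified as following".

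**The concern.** The table uses a four-grade scale but can fill only three of the grades. Suppose a participant has necrosis inside a small area of redness at the 20vPnC site. The e-diary may show that redness as mild. If redness and swelling stay under 5 measuring-device units, or a hospitalized participant makes no entries, the table shows no reaction or no value, and the participant also drops out of the cumulative counts. The worst reaction on the study's own scale would then look minor, or be absent, in a primary safety output.

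The AE route is not a like-for-like substitute:

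- The event is graded there on a different scale, so a Table 4 Grade 4 need not be an AE Grade 4.
- The window is 1 month instead of 10 days.
- AEs are summarized by preferred term, with no visible split by injection site, although every participant also receives SIIV in the other arm at Visit 1.
- A preferred term reported by fewer than 1% in both groups is Tier 3 and gets no between-group difference.

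At stake would be an understated severity profile for one of the primary safety endpoints.

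**Working it through.** **1. What the formula can return.** The e-diary can hold no grade or Grades 1 to 3, so the highest possible maximum is 3. For a participant with a CRF-recorded Grade 4 reaction:

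| Highest e-diary entry | Maximum under the SAP formula | Maximum if the CRF record were merged in |
|---|---|---|
| Grade 3 | 3 | 4 |
| Grade 2 | 2 | 4 |
| Redness or swelling under 5 units | no grade | 4 |
| No entries | no value | 4 |

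So the factual part of the concern holds on the visible text.

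**2. Whether the passages conflict.** They do not. Protocol 8.2.2.1, the footnotes to both grading tables, the three-level categorization in SAP 3.1.1 and the maximum-severity formula all tell the same story: the e-diary supplies mild, moderate and severe, and Grade 4 is an investigator-assessed AE. No visible sentence asks for the CRF record to be carried into the severity table.

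**3. Where a Grade 4 reaction is reported.**

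- AE tables by group, with n, N, percentage and Clopper-Pearson CI for all three tiers (SAP 6.1.1.3.1).
- Summaries and listings of severe, related and immediate AEs, where the event qualifies (SAP 3.1.1.4).
- SAE table and listing, if the participant was hospitalized (SAP 6.1.1.4.1).
- Immediate notification of the sponsor (protocol 8.2.2.1).

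**4. Scale.** The plan's sample size reproduces: 800 / (1 − 0.10) = 889 per group after rounding up, or 1778 in all, against about 1780 stated. The working figure is 890 per group, an upper figure for the safety population. The documents give no Grade 4 rate, so r per 20vPnC injection (one per participant) is an assumption. Expected events are 1780 × r, and the chance of at least one is 1 − (1 − r)^1780.

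| r (assumed) | Expected events | Chance of at least one |
|---|---|---|
| 0.01% | 0.18 | 16% |
| 0.05% | 0.89 | 59% |
| 0.1% | 1.78 | 83% |

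One event is 1/890 = 0.11% of a group. If a Grade 4 row existed, the Clopper-Pearson 95% CIs in a group of 890 would be 0 to 0.41% for no event, 0.00 to 0.62% for one and 0.03 to 0.81% for two.

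**5. Value of the missing comparison.** The Tier 2 threshold is 1% × 890 = 8.9, so nine participants in one group must report the same preferred term (8/890 = 0.90%, 9/890 = 1.01%). A rare Grade 4 term would therefore normally get no between-group CI. Had one been given, the Miettinen-Nurminen 95% CI for the difference would run from about −0.32 to +0.63 percentage points for 1/890 against 0/890, and from about −0.21 to +0.82 for 2/890 against 0/890. Neither tells the reader anything useful.

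**The case for a change.** The strongest case for a change is that the SAP defines a Grade 4 category for a primary safety endpoint and no visible output reports that category under its own name. AE tables use another scale and another window. A footnote, or one extra row for CRF-recorded Grade 4 reactions, would be cheap and would leave the e-diary derivation alone. Settling the matter before unblinding would also avoid any look of post hoc handling if a serious injection-site event occurred.

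Part of this stands. A reader of the table could be helped by a note that Grade 4 reactions are reported with AEs, and an analyst can add that note when building the table without amending the SAP.

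The stronger claim, that the table gives a wrong severity, does not stand. It assumes the table should combine both sources, which the documents never say. Merging would mix participant and investigator assessments and count one event under two endpoints. It would also need a CRF record that Table 4 Grade 4 was met. Sites are told to grade these AEs on the AE scale, and the CRF is not among the documents. The unscheduled-visit page (protocol 8.12) applies the local-reaction grades to pain only.

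The worst cases are possible but hypothetical. For pain, Grade 4 requires an emergency room visit or hospitalization for severe pain, so a severe entry in the e-diary, the table's top category, is the natural expectation.

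**Conclusion.** No change to the plan is needed. The visible formula stops at Grade 3, but this follows from a collection route that protocol and SAP describe consistently. Grade 4 reactions still reach the AE tables and listings and, where they qualify, the severe-AE, related-AE and SAE outputs. Followed as written, the plan supports a sound safety conclusion.

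The effect is at most 0.11 percentage points of a group per event. About 0.2 to 1.8 events are expected in the whole trial under assumed rates of 0.01% to 0.1% per 20vPnC injection. The table is descriptive; the noninferiority tests, alpha and power do not depend on it. What remains is a matter of table presentation.

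Two limits apply. The rates are assumptions with no source in the documents. Text is also redacted directly after the formula in SAP 3.1.1 and within SAP 6.1.1.1.1, so the plan cannot be said to lack a Grade 4 rule. For systemic events the maximum-severity formula is not visible at all, and nothing is concluded about it here.
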